5.5.9 Self-efficacy in dealing with bullying

KS2 pupils in both the intervention and UP arms will complete the PRQ [33] at Baseline and 12 Month follow-up. The scores from three items of this questionnaire will be averaged to give a measure of selfefficacy in defending bullying. As it is posited as another mechanism by which KiVa reduces bullying, this data will be used to determine if changes in rates of bullying are mediated by greater self-efficacy in defending bullying.

5.6 Tertiary/exploratory outcomes

5.6.1 School attendance, absences and exclusions

At baseline, schools will provide records of pupil-level authorised and unauthorised half-day absences. These data are routinely collected by schools for all pupils as a legal requirement. At 12 month follow-up, data from the Absence and Exclusion datasets will be requested from the National Pupil Database (NPD) for pupils in both the intervention and UP arms. At 12 Month follow-up, we will also request data from the KS2 attainment dataset from the NPD for pupils in both the intervention and UP arms.

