9.4.2 Consent/assent obtained at 12-Month follow-up

9.4.2.1 Parents/carers

Using the same distribution method as outlined in Section 9.4, parents and carers will receive an information leaflet requesting to provide consent to use additional information about their child to assist with the current trial's evaluation. This will include pupil-level data collected by the Department for Education and held on the NPD. Consent will also be sought to allow researchers to contact parents/carers in the future if there is a request to link children's trial data with other data. Consent will also be sought for parents to provide data about contact with the school about bullying by completing the bespoke Client Service Receipt Inventory (CSRI) [34]. Purposively selected parents and carers will receive an information leaflet about participating in qualitative interviews will also be asked to provide their written consent if they agree to take part. They will be informed that they will be offered a £20 voucher as reimbursement for their time.

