14.4 Missing, unused & spurious data

To investigate the impact of any missing outcome data on the trial conclusions, missing mechanisms will be explored, and appropriate imputation methods applied via sensitivity analyses. We will compare baseline characteristics and post-randomisation variables of pupils who have and have not completed primary outcome data. Multiple imputation will be performed to assess the impact of missing outcome data using the mi command in Stata. Imputation models will include outcomes (including pupil attendance), intervention arm, stratifying variables, and a main school effect to allow for clustering, as well as any appropriate baseline covariates. The main analyses will be repeated on the imputed datasets. As an added sensitivity analysis, a scenario-based imputation will be carried out such as best-worst case scenario assuming all lost to follow-up in the KiVa arm have been victimised and vice versa. Further details will be included in the statistical analysis plan (SAP), written prior to analysis.

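### Follow-up attendance comes only from NPD data, which need parental consent sought after allocation, so the 12-month attendance comparison rests on a subset selected after randomisation

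*Protocol*

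**What the plan says.** Investigating the effect on attendance is a tertiary/exploratory objective (Protocol, 5.3). Section 5.6.1 fixes the data source at each time point:

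- **Baseline:** "At baseline, schools will provide records of pupil-level authorised and unauthorised half-day absences". It adds: "These data are routinely collected by schools for all pupils as a legal requirement". Under 9.4.1.2, parents may file a 'right to object' form, so the baseline basis is opt-out.
- **Follow-up:** "At 12 month follow-up, data from the Absence and Exclusion datasets will be requested from the National Pupil Database (NPD"), in both arms. Section 12.2.2 repeats the NPD as the source and makes the timing depend on data release.

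The consent basis for the NPD data is in 9.4.2.1: "parents and carers will receive an information leaflet requesting to provide consent to use additional information about their child". On scope: "This will include pupil-level data collected by the Department for Education and held on the NPD". Section 15.3 confirms that linkage consent is requested at the follow-up data collection point and that linked data exist only where parents agree.

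Sections 14.6 and 15.1 restrict the main analyses to complete cases. Attendance has a second use in 14.4: "Imputation models will include outcomes (including pupil attendance"), alongside arm, stratifying variables and a school effect.

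**The concern.** The trial starts with school-held absence data on nearly all pupils and ends with data only on pupils whose parents agree to linkage. That agreement is sought after allocation is known and after one arm has lived with the programme for most of a school year. Section 11.3 describes a launch for parents and a parents' guide in KiVa schools, so the two sets of parents do not come to the consent request with the same experience of the trial.

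Randomisation protects a comparison of all pupils. It does not protect a comparison of those who remain after a selection step that the allocation can influence. If the parents who agree in one arm have children with systematically better or worse attendance than those who agree in the other, the analysis will show a difference that KiVa did not cause. The selection is also avoidable, because the protocol already has a route to the same information through the schools.

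**Working it through.** **1. Sources and consent side by side**

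| | Baseline | 12 months |
|---|---|---|
| Source | School records (5.6.1) | NPD (5.6.1, 12.2.2) |
| Consent basis | Opt-out, 'right to object' (9.4.1.2) | Opt-in parental consent (9.4.2.1, 15.3) |
| Timing (Table 1) | Feb-Apr 2020, before randomisation in May-June 2020 | Apr-Jun 2021, after allocation |

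No section has schools supply absences again at 12 months. The follow-up school pro-forma in 15.3 covers service use and contacts about bullying. The synopsis lists school attendance records together with the NPD datasets, but without time points, so it does not settle the matter.

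**2. How many pupils would remain**

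The protocol gives no expected linkage consent rate, so the rates here are assumptions. Of the 12,828 planned pupils:

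- 30% consent: 0.30 × 12,828 ≈ 3,848
- 50% consent: 0.50 × 12,828 = 6,414
- 70% consent: 0.70 × 12,828 ≈ 8,980

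**3. Possible bias on a standardised attendance scale**

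Assume no true effect. Let willingness to consent be a normal variable with correlation ρ to attendance, and let a fraction p consent. Mean attendance among consenters is then shifted by ρ × φ(z_p)/p SD, where z_p is the normal cut-off exceeded with probability p.

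- p = 0.5: 0.399/0.5 = 0.798
- p = 0.4: 0.386/0.4 = 0.966
- p = 0.3: 0.348/0.3 = 1.159

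The spurious difference between arms is ρ times the difference between these ratios:

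- ρ = 0.2, 50% v 40%: 0.2 × (0.966 − 0.798) = 0.034 SD
- ρ = 0.2, 50% v 30%: 0.2 × (1.159 − 0.798) = 0.072 SD
- ρ = 0.3, 50% v 30%: 0.3 × (1.159 − 0.798) = 0.108 SD
- Equal p and equal ρ in both arms: 0

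With ρ positive, the arm with the lower consent rate looks better.

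**4. The same point as a proportion**

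Assume 10% of pupils have high absence in both arms. Consent is c for all usual-practice pupils and for low-absence KiVa pupils, and c − d for high-absence KiVa pupils. The observed KiVa proportion is 0.10(c − d) / [0.10(c − d) + 0.90c].

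- c = 50%, d = 5 points: 0.045/0.495 = 9.1%, difference −0.9 points
- c = 50%, d = 10 points: 0.040/0.490 = 8.2%, difference −1.8 points
- c = 30%, d = 10 points: 0.020/0.290 = 6.9%, difference −3.1 points
- c = 70%, d = 10 points: 0.060/0.690 = 8.7%, difference −1.3 points
- d = 0: no difference

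**5. Imputation**

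Follow-up attendance would be missing from the 14.4 models for every pupil without linkage consent. Baseline attendance does not depend on that consent and stays available.

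**The case against.** The strongest reply has five parts.

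- **Source switch.** A reader might infer that mixing two sources biases the result. It does not do so by itself: both arms use the same source at each time point, and nothing defines attendance as change from baseline. What stands against the plan is smaller. A different source at follow-up weakens baseline adjustment and any change score.
- **Baseline coverage.** A reader might take the trial to hold baseline attendance on every pupil. Section 5.6.1 says only that schools hold it for all pupils, and parents may object to collection.
- **Imputation.** A reader might conclude that attendance becomes nearly useless for imputing the primary outcome. The documents do not support that. The imputation is a sensitivity analysis, it can use partly observed variables, and baseline attendance can enter it. The collection of the primary outcome does not depend on NPD consent.
- **Size.** Every consent rate and correlation above is assumed. One consent process applies to both arms, and a launch and a guide for parents do not show that consent will differ. Adjusting for baseline absence would also absorb selection that acts through earlier attendance, which the formula ignores. All of this is fair. It limits what can be said about size but does not remove the exposure.
- **The remedy.** School records will be incomplete for leavers (section 10.2 cites 6% turnover for England), whereas NPD linkage works on name and date of birth. It is also unresolved whether the 'right to object' basis covers follow-up absence records. Both points stand and are taken into the fix.

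**Conclusion.** The point holds for attendance as an exploratory outcome. As written, the 12-month comparison is limited to pupils whose parents opt in after allocation, and it is open to bias if consent differs by arm in a way related to absence. Under the assumed consent rates (50% against 30% to 40%) and correlations (0.2 to 0.3), the spurious difference is about 0.03 to 0.11 SD. It is zero if consent is equal across arms and related to absence in the same way in each. The protocol gives nothing from which to choose within that range.

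It would go too far to say that the primary result is threatened. The only link is through the sensitivity imputation, where follow-up attendance would be missing for non-consenters. The case for a change rests on the selection being avoidable at low cost.

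**What to change.** In Protocol sections 5.6.1 and 12.2.2:

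- Collect pupil-level half-day absences from school records at 12 months, as at baseline, for all pupils without a 'right to object' form. First confirm that the approvals and the information given to parents cover this.
- Use these records as the attendance outcome and as the attendance variable in the imputation models of 14.4.
- Keep the NPD for attainment and exclusions. Use NPD absence as a cross-check, and for consenting pupils who have left the school.
- Report linkage consent by arm, with baseline absence of consenters and non-consenters. The NPD-only outcomes need this in any case.

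The cost is a short amendment and administrator time for one more extract of a kind that schools already provide. Under 9.4.1.4, administrators supply school data once the headteacher has consented. School records will remain incomplete for leavers.

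If the approvals cannot be extended, the consent report by arm is the minimum, and the attendance result should be described as applying to consenters only.

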5.6.2 Participant role in bullying

KS2 pupils in both the intervention and UP arms will complete the PRQ [33] at Baseline and 12 Month follow-up. The questionnaire identifies five scales that describe the different roles in bullying; the bully scale, the assistant scale, the reinforcer scale, the defender scale and the outsider scale. The respondent is asked to rate how often they behave in the ways described for each of the roles on a three-point scale (Never, Sometimes, Often).

5.6.3 SES and gender

At baseline, school-level FSM eligibility and gender will be obtained from the school and/or online databases such as http://statswales.gov.wales and https://www.gov.uk/search/research-and-statistics.

5.6.4 Intervention implementation and mechanisms

The fidelity data will help to interpret trial outcomes. For instance, if KiVa is not found to be effective this may be because of low levels of coverage. Understanding intervention mechanisms may also help to explain and understand trial outcomes e.g. we may observe unintended consequences of introducing KiVA into school systems. Process evaluation will also help to determine whether there are relationships between fidelity/quality of delivery and outcomes.

5.6.4.1 KiVa implementation fidelity

KiVa lesson implementation fidelity will be assessed in all intervention schools using online or paperbased Teacher Lesson Record Books completed by teachers after each KiVa lesson. KiVa Lesson Record Books will collect information on teacher number of lessons delivered (a proxy for intervention adherence), length of lessons, teacher preparation time, components delivered, lesson quality and student engagement. All intervention schools will complete a checklist to assess adherence to the schoolwide KiVa elements.

Fidelity will also be assessed through observations at a purposively sampled group of 16 intervention schools. For these schools, research assistants will also complete the Lesson Record book and checklist to assess reliability of teacher-reported lesson and schoolwide implementation fidelity. We will also collect redacted KiVa forms used for confirmed incidents of bullying.

5.6.4.2 Factors influencing KiVa implementation

Factors influencing KiVa implementation will be explored through in-depth interviews with teachers involved with KiVa delivery from eight intervention schools around 12 Month follow-up.

5.6.4.3 KiVa intervention mechanisms

Intervention mechanisms will be explored in focus groups with pupils and through one-on-one interviews with parents/carers of eight intervention schools around 12 Month follow-up. Parents/carers who are interviewed will be offered a £20 voucher as reimbursement for their time. Observation of lesson and school-wide delivery, and implementation of indicated actions will also be used to explore intervention mechanisms.

5.6.5 Usual antibullying practices

UP will be assessed in both intervention and control schools at Baseline and 12 Month follow-up by collecting a copy of the schools' bullying policy, interviews with the schools' Headteacher and through completion of a trial specific checklist.

6 Trial design and setting

This is a parallel-group, multicentre, two-arm, cluster RCT, with process and economic evaluations. One hundred and sixteen non-fee-paying primary schools will be recruited from four geographical areas coordinated through four Universities (hubs): North Wales (Bangor University), West Midlands (University of Warwick), South East England (University of Oxford) and South West England (University of Exeter). Schools (sites) will be randomised to receive KiVa over one academic year or continue with UP. The effectiveness and cost-effectiveness of KiVa will be assessed 24-months after randomisation.

6.1 Risk assessment

A Trial Risk Assessment has been completed to identify the potential hazards associated with the trial and to assess the likelihood of those hazards occurring and resulting in harm. This trial has been categorised as a low risk where the level of risk is comparable to the risk of usual antibullying practices in schools. A copy of the trial risk assessment may be requested from the CTR.

6.2 Participant risks

Potential risks of the intervention to participants are minimal. Some individuals might find aspects of the intervention content or research upsetting if they have experience with bullying victimisation or perpetration. Trial managers will work with schools to ensure a system is in place to enable appropriate support to be provided in such circumstances. Any potential for harmful effects due to the intervention itself will be explored via the collection and analysis of qualitative data to explore unintended consequences.

7 Site and Investigator selection

This trial will be carried out at participating primary schools within Wales and England. Headteachers who are interested in registering their school in the trial will sign an agreement to confirm that they have adequate resources to complete the trial.

Before any site can begin recruitment a Principal Investigator at each site must be identified. The following documents must be in place and copies sent to the Stand Together trial email account (see contact details on page 4):

- > Favourable opinion from Main Ethics committee
- A signed Trial Agreement
- > Current Curriculum Vitae and GCP training certificate of the Principal Investigator (PI)
- > Completed Site Delegation Log and Roles and Responsibilities document
- > Full contact details for all Site (Institution) personnel involved, indicating preferred contact
- A copy of the most recent approved version of the Participant Information Sheets and Consent Forms on host care organisation headed paper
- Returned copy of the Self-Evident Correction Log signed by the PI.

Upon receipt of all the above documents, the Trial Manager will send written confirmation to the Principal Investigator detailing that the centre is now ready to recruit participants into the trial. This letter/email must be filed in each site's Site File.

Occasionally during the trial, amendments may be made to the trial documentation listed above. CTR will issue the site with the latest version of the documents as soon as they become available. It is the responsibility of the CTR to ensure that they obtain ethics approval for the new documents. Site initiation will be by teleconference.

8 Participant selection

Schools are eligible to participate in the trial if they meet all the following inclusion criteria and none of the exclusion criteria apply. All queries about participant eligibility should be directed to the Trial Manager before randomisation/registration.

8.1 Inclusion criteria

Mainstream, state primary schools (up to Year 6) with at least two KS2 classes.

8.2 Exclusion criteria

Ineligible schools are those that:

- Are mixed primary and secondary schools
- Delver education through a language other than English or Welsh
- Already implement a recognised anti-bullying programme that is considered to extend beyond a standard approach
- Have already implemented KiVa
- Cater solely for pupils with special educational needs (i.e., Special schools)
- Do not have leadership that can guarantee project participation for the year of data collection/implementation

9 Recruitment, Screening and registration

9.1 Identification of schools

A list of eligible schools in each geographical area will be identified by accessing publicly available information on the schools' or government website, from which the schools' contact details will also be obtained. Schools may also be identified through education conferences, Regional School Effectiveness and Improvement Service for North Wales, Birmingham Education Trust and the Schools Health Research

Network in Wales and Public Health leads for schools in local authorities in England. Schools' senior manager (deputy head, head of pastoral care) of eligible schools will be leafletted via email. All sites will be recruited in the area local to the hub to facilitate data collection and school required support.

9.2 Screening logs

A screening log of all ineligible and eligible but not consented/not approached schools will be kept at each hub so that any biases from differential recruitment will be detected. When at the hub, logs may contain identifiable information, but this **must** be redacted prior to being sent to the CTR. The screening log should be sent to the [contact] every week (see section 19 for further detail on data monitoring/quality assurance).

9.3 Recruitment rates

Sites will be recruited at an expected rate of three per week per hub in order to reach the recruitment target of 116 schools by May 2020.

9.3.1 Progression criteria

Recruitment rates of schools and pupils across the four hubs will be used to determine trial feasibility. Progression to a full trial in all sites will dependent upon recruitment progress. Progression thresholds are set out below, with early cessation if the lower targets are not achieved. The decision to continue will be made at the end of May 2020. However, should the trial be terminated all interested schools will have the opportunity to be trained and implement KiVa on the same basis as all other schools across the UK.

Green (continue to full trial without modification):

- 90% or more of target schools recruited
- 80% or more eligible pupils recruited
- 90% or more baseline primary outcome collected
- 80% or more baseline secondary outcomes collected

Amber (remediable issues; proceed with caution): Review processes with the Trial Steering Committee and PPI group to see if we could improve before a recommendation is taken on progression.

• 80- 89% of schools recruited

- 60-79% eligible pupils recruited
- 80-89% baseline primary outcome collected
- 65-79% baseline secondary outcomes collected

Red: the TMG will consult with NIHR PHR for advice on how the trial should proceed

- Less than 69% schools recruited
- Less than 59% eligible pupils recruited
- Less than 79% baseline primary outcome collected
- Less than 64% baseline secondary outcome collected

9.4 Informed consent

To protect potential participants' (pupils' and parents') privacy, the school will disseminate information sheets, 'right to object' forms and consent forms to parents/carers on the researchers' behalf. Materials will be distributed using the schools' usual communication system. For instance, some schools will use electronic 'parent mail' and others may use paper newsletters. We will request that school uses alternative methods of contact to inform any parents/carers who do not receive information using normal communication systems. We will also ask the school to display trial information on schoolwide forums e.g. school bulletins to ensure that all parents/carers of KS2 children are informed about the trial and have been provided with an opportunity to complete a 'right to object' form.

Potential participants will be able to keep the information sheet (except for pupils; who will not be provided with a written information sheet) which will provide details of who to contact if they require further information about the research or bullying. The right of the potential participant to refuse to participate without giving reasons will be respected. Just prior to conducting the trial assessments, the researcher will inform all participants that they can withdraw their consent/assent up until the data has been collected and the interviews have been conducted. After this, data will not be able to be withdrawn as it will be pseudonymised.

9.4.1 Consent/assent obtained at Baseline

9.4.1.1 Headteacher

Headteachers will receive a leaflet which will provide information about the trial, what is involved, time commitment, costs, benefits and information on pupil privacy and safety. Headteachers will be directed to the Stand Together trial website if they wish to obtain more information. If the headteacher wishes to register their school in the trial, they will be required to agree to the terms stipulated in the agreement and provide their written consent.

9.4.1.2 Parents/carers

Information leaflets will be distributed to parents/carers of children at participating schools. Parents/carers will be informed that they have the 'right to object' to their child's data being collected and will be able to complete and return the 'right to object' form if they do not want their child to complete questionnaires to be used in the trial evaluation.

